4.2.1.2.5 Duration

Duration is derived from the start and end dates of the unsolicited AE:

- Duration = End date of unsolicited AE - start date of unsolicited AE + 1.

The duration is considered as missing only if one or both of the start and end dates of the unsolicited AE is missing or partially missing.

4.2.1.2.6 Medically-Attended Adverse Event

An event will be considered as an MAAE if “Yes” is checked for “Is the event an MAAE?” in the CRF. MAAE will be analyzed within 21 days after vaccination, from D22 to 180 days after vaccination, and within 180 days after vaccination.

4.2.1.2.7 Serious Adverse Events

An event will be considered as a serious event if “Yes” is checked for “Serious” in the CRF.

SAEs will be analyzed within 21 days after vaccination, from D22 to 180 days after vaccination, and within 180 days after vaccination.

4.2.1.2.8 Adverse Events of Special Interest

An event will be considered as an AESI if “Yes” is checked for “Is the event an AESI?” in the CRF.

AESIs will be analyzed within 21 days after vaccination, from D22 to 180 days after vaccination, and within 180 days after vaccination.

4.2.2 Other Safety Endpoints

4.2.2.1 Pregnancy

Not applicable

4.2.2.2 Action Taken

This information will be summarized as collected, including missing observations. No derivation or imputation will be done.

4.2.2.3 Seriousness

This information will be summarized as collected. No derivation or imputation will be done.

4.2.2.4 Outcome

This information will be summarized as collected. No derivation or imputation will be done.

4.2.2.5 Causal Relationship

This information will be summarized as collected in the field “Relationship to study vaccine”. Missing causal relationship will be handled as described in Section 3.4.4.1.2. Relationship to study procedure is only presented in the listing.

4.2.2.6 Adverse Events Leading to Study Discontinuation

This information will be summarized as collected. A flag is available in the clinical database for all AEs in order to identify AEs leading to discontinuation before the end of active phase.

In general, the items that are counted are:

- Disposition table: A participant who, on the “Completion at End of Active Phase” form question “What was the participant's status?” has “Adverse Event” checked.
- Safety overview table: A participant who has either on the “Completion at End of Active Phase” form, question “What was the participant's status?” has “Adverse Event” checked or lists a solicited AE that has “Caused Study Termination” checked that is at least Grade 1 or an unsolicited AE that has “Caused Study Discontinuation” checked that is at least Grade 1 or missing and is within the time period indicated.
- System Organ Class (SOC)/Preferred Term (PT) table: A solicited AE that has “Caused Study Termination” checked that is at least Grade 1 or an unsolicited AE that has “Caused Study Discontinuation” checked that is at least Grade 1 or missing and is within the time period indicated.

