- ‡ BL0001 must be collected before vaccine injection. Participants that consent to Future Research by ticking the corresponding box in the ICF will provide a 20 mL of blood instead of 10 mL for each BL0001 and BL0002.
- § Participants will use DC1 to record information about solicited reactions, unsolicited AEs, SAEs, and AESIs from D01 to D08 after vaccination and will continue to record information about unsolicited AEs, SAEs, and AESIs from D09 to D22.
- ** The Investigator or an authorized designee will remind the participants to bring back the DC at the next visit and will answer any questions.
- †† The Investigator or an authorized designee will interview the participants to collect the information recorded in the DC1 and will attempt to clarify anything that is incomplete or unclear.
- ‡‡ During this call the staff will review the MA with the subject and determine whether the subject experienced any SAE, AESI or MAAEs not yet reported.
- §§ AESIs (serious and non-serious) will be collected throughout the study as SAEs to ensure that events are communicated to the Sponsor in an expedited manner and followed up until the end of the follow-up period or resolution, as per the assigned causal relationship. Full list of AESIs is available in [Section 8.3.6](#).
- *** Participants will be in the Active Phase from enrollment (D01) until completion of V02 and in the 6-Month Safety Follow-Up from completion of V02 until approximately 6 months after V01.

2 Introduction

Fluzone® High-Dose Quadrivalent (*Influenza Vaccine*)

Fluzone High-Dose Quadrivalent vaccine is an inactivated influenza vaccine containing 60 mcg of hemagglutinin (HA) of each of the A strains (A/H1N1 and A/H3N2) and of each of the B strains (from the Victoria lineage and from the Yamagata lineage), in compliance with the seasonal influenza World Health Organization (WHO). A recent systematic review and meta-analysis, including over 34 million participants and over 10 influenza seasons, showed that irrespective of circulating strain and antigenic match, the high-dose inactivated trivalent influenza vaccine is more effective than standard-dose vaccine in preventing both influenza-like illness and influenza-related hospitalizations in both controlled and real-world conditions (1). Fluzone High-Dose Quadrivalent vaccine is indicated for active immunization for the prevention of influenza in persons 65 years of age and older.

Moderna COVID-19 Vaccine (mRNA-1273 vaccine)

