* For all reactions (except fever), the scale will be provided in the CRF and the intensity will be transcribed from the diary card. For fever, the body temperature will be recorded, and the classification as Grade 1, 2, or 3 will be assigned at the time of the statistical analysis based on the unit used to measure the temperature and the intensity scale.

Important notes for the accurate assessment of temperature:

Participants are to measure body temperature once per day, preferably always at the same time. The optimal time for measurement is the evening, when body temperature is the highest. Temperature is also to be measured at the time of any apparent fever. The observed daily temperature and the route of measurement are to be recorded in the diary card, and the highest temperature will be recorded by the site in the CRF. The preferred route for this study is oral.

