3.4.4.1.3 Intensity

For solicited reactions, missing intensities will be handled as described in Section 4.2.1.1.1. For unsolicited AEs, missing intensities will remain missing and will not be imputed.

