4.2.1 Safety

4.2.1.1 Solicited Reactions

4.2.1.1.1 Daily Intensity

All daily records for solicited reactions will be derived into daily intensity according to the following classification: None, Grade 1, Grade 2, Grade 3, or Missing (Unknown).

For the derivation of daily intensities, the following sequential steps will be applied:

- 1) Solicited reactions (except Fever/Pyrexia) with CRF presence recorded as “No” and with all daily records missing (Unknown) then all daily intensities will be derived as None.
- 2) For non-measurable solicited reactions, daily intensities will correspond to daily records reported in the clinical database. For measurable solicited reactions the daily measurements reported in the clinical database will be converted based upon the intensity scales defined in the protocol; this assumes a reaction that is too large to measure (non-measurable, “NM”) is Grade 3. Note the intensity could be considered “None” (not a reaction) in the analysis despite being considered a reaction by the investigator (e.g., swelling measurement > 0 mm but < 25 mm in adults).

Note: The maximum intensity on the ongoing period is derived from the record of the maximum intensity/measurement after the end of the solicited period following the rule described above.

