4.2.1.1.3 Presence

Presence is derived from the maximum overall intensity over the time period considered:

- None: No presence

- Grade 1, Grade 2, or Grade 3: Presence
- Missing or Unknown: Missing presence

Participants with at least one non-missing presence for a specific endpoint will be included in the analysis. Conversely, those without a non-missing presence will not be included in the analysis of the endpoint.

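### The SOC/PT table of AEs leading to discontinuation drops a flagged solicited reaction that has no grade on any day, but keeps a flagged unsolicited AE with a missing grade

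*SAP*

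**What the plan says.** SAP 4.2.2.6 lists three outputs.

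- **Disposition table:** counts a participant whose status on the end-of-active-phase completion form is Adverse Event.
- **Safety overview table:** counts a participant by that status or by a qualifying flagged AE.
- **SOC/PT table:** counts qualifying flagged AEs only; the completion form plays no part.

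The conditions on a flagged AE are worded alike in the overview and SOC/PT bullets. A solicited AE must be "checked that is at least Grade 1 or an unsolicited AE that has" its own discontinuation flag, and that unsolicited AE must be "checked that is at least Grade 1 or missing and is within the time period indicated". A missing grade is thus accepted for unsolicited AEs and not mentioned for solicited ones.

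Three other SAP rules bear on an ungraded event:

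- SAP 4.2.1.1.1: a solicited reaction (other than fever) recorded in the CRF as not present "and with all daily records missing (Unknown) then all daily intensities will be derived as None". There is no matching rule for a reaction recorded as present.
- SAP 4.2.1.1.3: "Missing or Unknown: Missing presence", and "Conversely, those without a non-missing presence will not be included in the analysis of the endpoint".
- SAP 3.4.4.1.3: "For unsolicited AEs, missing intensities will remain missing and will not be imputed". Under SAP 4.2.1.2.1 an unsolicited AE is still an event if it has a verbatim term and is not Grade 0.

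On where the grade comes from, Protocol 10.2.5.1.1 says for pain and for all systemic reactions except fever that "the scale will be provided in the CRF and the intensity will be transcribed from the diary card". Table 1.1 has the diary card collected at V02 (D22). At the D08 call its footnote says: "The Investigator or an authorized designee will remind the participants to bring back the DC at the next visit", and to answer questions.

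**The concern.** Of the three outputs, the SOC/PT table is the only one that says which event made a participant leave. For solicited reactions, inclusion depends on a derived grade as well as on the investigator's flag, and that grade comes mainly from a diary collected at V02. A participant who leaves before V02 because of a reaction may not return the diary. The site could then know which reaction it was, and flag it, without holding a grade for any day.

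If so, the overview and disposition tables would show a discontinuation due to an AE while the SOC/PT table shows no event for that participant. The same record classed as unsolicited would be shown. What is at stake is the reconciliation of three small safety tables and the naming of the cause.

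**Working it through.** **1. Apply the SOC/PT rule to a flagged event, by type and grade**

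| Grade of flagged event | Solicited | Unsolicited |
|---|---|---|
| None | not counted | not counted |
| Grade 1, 2 or 3 | counted | counted |
| Missing | **not counted** | **counted** |

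The two limbs differ in the last row only.

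**2. Look for another rule that rescues the missing solicited grade**

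- SAP 3.4.4.1.3 refers missing solicited intensities to SAP 4.2.1.1.1.
- SAP 4.2.1.1.1 resolves wholly missing daily records only where CRF presence is No, and sets them to None. Present but ungraded is not covered, so the intensity stays missing.
- SAP 4.2.1.1.2 takes the maximum over the days. One graded day is enough to keep the event; with no graded day the maximum is missing.
- SAP 4.2.1.1.3 then makes presence missing and removes the participant from that endpoint.

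Nothing rescues the event.

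**3. Compare with the SAP's other conventions for missing safety data**

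- A missing causal relationship of an unsolicited systemic AE is taken as related (SAP 3.4.4.1.2).
- An unsolicited AE with missing onset is included in the 21-day analysis (SAP 4.2.1.2.4).
- A flagged unsolicited AE with missing grade is included (SAP 4.2.2.6).
- SAP 4.2.2.6 itself opens by saying that the information is reported the way it was recorded, and that the database holds a flag for this purpose for all AEs.

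Only the solicited limb lets a missing derived grade override the flag, and the SAP gives no reason for it.

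**4. Trace one such participant through the three tables**

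| Completion status | Disposition (as AE) | Overview | SOC/PT |
|---|---|---|---|
| Adverse Event | counted | counted, by the form | no event |
| Other, such as Withdrawal by Participant | not counted | not counted | no event |

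The second row is possible because Protocol 7.2 lists several withdrawal reasons, of which one is recorded.

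**5. Scale**

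Inputs: about 100 per group and 5% dropout (Protocol 9.2). The plan's own figure reproduces: 100 × (1 − 0.05) = 95 evaluable, so 5 dropouts per group from all causes. If dropout is as assumed, 5 is the ceiling, reached only if every dropout left over a flagged, ungraded solicited reaction. The documents do not give the actual number; 0 to 2 per group is an assumption.

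Exact (Clopper-Pearson) 95% limits for x of n: lower = Beta⁻¹(0.025; x, n − x + 1), upper = Beta⁻¹(0.975; x + 1, n − x), with lower = 0 when x = 0. For n = 100:

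| Events lost from the table | True row | 95% CI |
|---|---|---|
| 0 | 0/100 = 0% | 0% to 3.62% |
| 1 | 1/100 = 1% | 0.03% to 5.45% |
| 2 | 2/100 = 2% | 0.24% to 7.04% |
| 5 (ceiling) | 5/100 = 5% | 1.64% to 11.28% |

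Under the present rule the row would read 0/100 in every case if these were the only events. The intervals show scale only: SAP Table 3.1 plans CIs for main endpoints, and nothing says that this table will carry them.

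**The case against.** **The record needed is unusual.** It must name the reaction, carry the flag and have no grade on any day. If the diary is lost and the site learns nothing, there is no flagged record to rescue. If the site knows enough to flag the reaction, it may well be able to grade it: Protocol 10.2.5 requires a grade for each AE, Protocol 8.3.2 lets sites report information that is not in the diary, and Protocol 7.2 asks them to contact most early leavers. There is also a call on D08. This stands, and it limits the point to wholly ungraded reactions. It does not remove it: the SAP makes explicit provision for missing grades, and a participant may decline further contact.

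**The asymmetry follows from the SAP's definitions.** Solicited presence is derived from intensity, and unsolicited presence from the verbatim term. That probably explains the wording. It does not justify using a missing grade to set aside the investigator's statement that the reaction ended participation.

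**The change moves the inconsistency.** An ungraded reaction would appear in SOC/PT while its presence stays missing in the solicited-reaction tables. This is true, and it is a small cost that a footnote can cover.

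**A reader might infer** that the table loses everyone who leaves over a reaction and does not return the diary, or that it is materially biased toward zero. The documents do not support either. One graded day keeps the event, grades can be obtained without the diary, and no count of affected participants is given.

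**Conclusion.** The point holds in a narrow form. In the SOC/PT table of SAP 4.2.2.6, a solicited reaction that is named, flagged and ungraded on every day is dropped, whereas an unsolicited AE in the same state is kept. Because that table does not use the completion form, it can fail to reconcile with the disposition and overview tables.

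The expected number is very small. Protocol 7.2 expects withdrawal to be uncommon, and the 5% dropout assumption covers all reasons. Discontinuation due to AEs is not among the endpoints in Protocol Table 3.1 or SAP Table 2.1, and neither the sample size nor any immunogenicity result is affected. This is a minor reporting defect, worth correcting because the correction is nearly free.

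The conclusion rests on reading 4.2.2.6 as written, and on the assumption that a solicited AE record can be flagged without a grade, which the SAP does not exclude.

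**What to change.** In the SOC/PT bullet of SAP 4.2.2.6, change the condition on a flagged solicited AE to *at least Grade 1 or missing*, as for unsolicited AEs. The flag then decides inclusion whenever the grade is unknown. Events derived as None stay out, including those with CRF presence No and measurements under 25 mm.

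Make the same edit in the overview bullet, for consistency and for participants whose completion status is not Adverse Event.

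Add a footnote to the SOC/PT table: a reaction included with a missing grade has missing presence under SAP 4.2.1.1.3 and so does not appear in the solicited-reaction tables.

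Cost: two words in each of two bullets, one programming condition and one footnote. No new data are needed.

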4.2.3 Immunogenicity

4.2.3.1 Computed Values for Analysis

For the derivation of immunogenicity endpoints, all values strictly under the lower limit of quantification (LLOQ) will be treated as LLOQ/2, and all values above or equal to the upper limit of quantification (ULOQ) will be treated as ULOQ.

For the analysis of the results of HAI assay which is performed in duplicate, the individual geometric mean (GM) of both values will be computed for each blood sample and each strain,

after managing extreme values as described above. The computed value is then considered the titer for that particular blood sample.

For the analysis of SARS COV-2 immune response, the serological results will be received in ELU/mL (ELISA Laboratory Unit) but will be expressed in BAU/mL (Binding Antibody Unit) for the analysis. The following formula will be used for converting the concentration units from ELU/mL to BAU/mL:

$$\text{Result (BAU/mL)} = \text{Result (ELU/mL)} / 7.9815$$

4.2.3.2 Fold-rise

For the HAI and SARS COV-2 immune response, the derived endpoint fold-rise is driven by both baseline (D01) and post-baseline (D22) computed values as described in Section 4.2.3.1 and is computed as individual ratio:

- 21 days after vaccination divided by D01.

For the SARS COV-2 immune response:

- If the computed fold-increase is ≥ 2 , the derived ≥ 2 -fold rises indicator will be “Yes”, otherwise ≥ 2 -fold rises will be “No”.
- If the computed fold-increase is ≥ 4 , the derived ≥ 4 -fold rises indicator will be “Yes”, otherwise ≥ 4 -fold rises will be “No”.

Note: if pre-vaccination (D01) or post-vaccination (D22) values is missing, the fold-rise is missing.

4.2.3.3 Seroconversion

For HAI assay, seroconversion is defined as a binary indicator. If a pre-vaccination (D01) titer < 10 (1/dil): post-vaccination titer ≥ 40 (1/dil) on 21 days after vaccination (D22), or ≥ 4 -fold-rise for participants with a pre-vaccination titer ≥ 10 (1/dil), the derived seroconversion indicator will be “Yes”, otherwise will be “No”.

Note: if pre-vaccination (D01) or post-vaccination (D22) value is missing, the seroconversion is missing.

4.2.4 Derived Other Variables

4.2.4.1 Age for Demographics

The age of a participant in the study will be the calendar age in years at the time of inclusion, as collected in the eCRF.

For randomization stratification and subgroup analyses, the 2 following classes of age will be used: < 75 years and ≥ 75 years.

5 Changes in the Conduct of the Trial or Planned Analyses

This section summarizes major changes in the SAP amendment.

Table 5.1: Major statistical changes in SAP amendment

Amendment Number	Approval Date	Changes	Rationale
Amendment 1 (SAP v2.0)		Addition of 6-month f-up analysis	Protocol Amendment 2

6 Supporting Documentation

6.1 Appendix 1 List of Abbreviations

AE	Adverse Events
AESI	Adverse events of special interest
AR	Adverse reactions
BAU	Binding Antibody Unit
CRF	Case report form
ELU	ELISA Laboratory Unit
GCP	Good Clinical Practice
GM	Geometric mean
GMT	Geometric mean of titer
GMC	Geometric mean of concentration
LLOQ	Lower level of quantitation
MAAE	Medically attended adverse event
MedDRA	Medical Dictionary for Regulatory Activities
NA	Not applicable
RCDC	Reverse cumulative distribution curve
SAE	Serious adverse events
SafAS	Safety analysis set
SAP	Statistical analysis plan
SOC	(Primary) System organ class
PT	Preferred term
TC	Telephone Contact
ULOQ	Upper level of quantitation

7 References

1. Newcombe RG. Two-sided confidence intervals for the single proportion: comparison of seven methods. *Stat Med*. 1998;17(8):857-72.
